### **2.4 Study Endpoints**

The study contains a single treatment arm with subjects receiving the Neuroform Atlas™ Stent. The primary endpoints will be evaluated for all subjects treated with this investigational device.

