### **2.4.1 Primary Endpoints**

#### **2.4.1.1 Primary Effectiveness Endpoint**

The primary effectiveness endpoint of the study is:

Complete aneurysm occlusion (100% occlusion – Raymond Class 1) of the treated target lesion on 12 month angiography, in the absence of retreatment, or parent artery stenosis (>50%) at the target location.

The Raymond Class 1 designation of complete occlusion (**Figure 1**) will be used to define occlusion success.

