# **Safety and Effectiveness of the Treatment of Wide Neck, Saccular Intracranial Aneurysms with the Neuroform Atlas™ Stent System**

## **Short Study Name: ATLAS**

screening log. In all cases where subjects are consented but not treated using a Neuroform Atlas™ Stent, replacement subjects will be enrolled. Subjects in whom an investigational procedure is attempted but stent delivery is unsuccessful will be followed through the two month follow-up visit; these subjects will be considered treatment failures but will not be evaluated for the primary endpoints at 12 months. All treated subjects with successful stent delivery and deployment will be evaluated for the primary endpoints at 12 months post-procedure.

For long-term follow-up, subjects will be asked to return for clinical follow-up visits at 2 years and 3 years ( $\pm$  6 months) post-index procedure.

The study flow is depicted in **Figure 2**.

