# **Safety and Effectiveness of the Treatment of Wide Neck, Saccular Intracranial Aneurysms with the Neuroform Atlas™ Stent System**

## **Short Study Name: ATLAS**

### **4.4 Analysis Populations**

**ITT (Intent to Treat):** All subjects who have signed the Informed Consent Form for this trial, and in whom the Neuroform Atlas™ Stent implantation procedure has been attempted (i.e., a component of the stent system was introduced into the body).

**mITT (Modified Intent to Treat):** All subjects who have signed the Informed Consent Form for this trial, and in whom the Neuroform Atlas™ Stent has been successfully implanted.

**PP (Per Protocol):** All subjects who have signed the Informed Consent Form for this trial, who have had the Neuroform Atlas™ Stent successfully implanted, and who have not been the subject of any major protocol deviations.

**Enrolled Not Treated:** All subjects who have signed the Informed Consent Form for this trial, but in whom no component of the Neuroform Atlas™ Stent System has ever been introduced into the body as part of an implantation procedure.

**PAS ITT (ITT for the PAS):** All subjects who have signed the Informed Consent Form for this trial, and in whom the Neuroform™ Atlas Stent has been successfully implanted. This cohort is identical to the mITT cohort.

**PAS mITT (Modified Intent to Treat in PAS):** All mITT subjects who have not withdrawn, died, or refused follow-up.

The primary safety and effectiveness analyses will be performed on the mITT population. The 95% Confidence Interval (CI) for each endpoint will be calculated using the exact binomial distribution. In addition, safety data will include any adverse events reported to occur among ITT subjects in whom a Neuroform Atlas™ Stent implantation procedure was attempted but did not successfully occur. For long-term follow-up, all analyses completed for the PAS mITT cohort will also be completed for the PAS ITT cohort for comparison

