Analyses for both cohorts will be performed by constructing two-sided 95% confidence intervals about the estimates of the percentage of subjects with complete aneurysm occlusion and the percentage of subjects experiencing a major ipsilateral stroke or neurological death using the exact binomial (Clopper-Pearson) method. For the effectiveness endpoint of total occlusion, the lower bound of this confidence interval will be compared to 50% for both the anterior and posterior circulation cohorts. For the safety endpoint of major ipsilateral stroke and neurological death, the upper bound of the confidence interval will be compared to 20% for the anterior circulation cohort, and 25% for the posterior circulation cohort.

Success requires safety and effectiveness endpoints to be met in each cohort separately. Success in the anterior cohort occurs when the lower bound of the effectiveness endpoint is above 50% and the upper bound of the safety endpoint is below 20%. Success in the posterior cohort occurs when the lower bound of the effectiveness endpoint is above 50% and the upper bound of the safety endpoint is below 25%.

The analysis of long-term safety and effectiveness data will be descriptive only, as no formal hypotheses will be tested based on data collected during this phase of the study. Survival analysis will be used to estimate the incidence of specified safety endpoint events, as well as retreatment of the target aneurysm. Details regarding the survival analyses are summarized in **Table 7**.

**Safety and Effectiveness of the Treatment of Wide Neck, Saccular Intracranial Aneurysms with the Neuroform Atlas™ Stent System**

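### Both primary endpoints are decided on successful implants only, and the defined ITT set has no primary-endpoint analysis, so failed deliveries enter no interval compared with a goal

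*Combined protocol and SAP*

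**What the plan says.** Section 4.4 defines mITT as consented subjects with a successfully implanted stent, and ITT as consented subjects "in whom the Neuroform Atlas™ Stent implantation procedure has been attempted (i.e., a component of the stent system was introduced into the body". It then assigns the deciding analyses: "The primary safety and effectiveness analyses will be performed on the mITT population". Its one further use of the failed attempts is that "safety data will include any adverse events reported to occur among ITT subjects in whom a Neuroform Atlas™ Stent implantation procedure was attempted" without success; no interval or goal is attached.

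Section 2.6 deals with failed deliveries directly: "Subjects in whom an investigational procedure is attempted but stent delivery is unsuccessful will be followed through the two month follow-up visit", and "these subjects will be considered treatment failures but will not be evaluated for the primary endpoints at 12 months".

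Section 4.6 sets the decision rules with two-sided 95% Clopper-Pearson intervals. The effectiveness lower bound must exceed 50% in both cohorts. For safety, "the upper bound of the confidence interval will be compared to 20% for the anterior circulation cohort" and with 25% for the posterior cohort.

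The endpoint wording leans the same way as the mITT choice. Section 2.4 says "The primary endpoints will be evaluated for all subjects treated with this investigational device", and section 2.4.1.1 assesses occlusion "of the treated target lesion on 12 month angiography, in the absence of retreatment".

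**The concern.** Membership of mITT depends on how the procedure went. In a single-arm trial judged against fixed goals, no control arm offsets that selection. If the result is read as applying to every patient in whom the stent is attempted, the effectiveness rate is too high by roughly the delivery-failure fraction. A major ipsilateral stroke or neurological death after a failed attempt is missing from the primary safety proportion.

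No other planned analysis supplies the missing result:

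- Technical success (section 2.4.2.1) and the stent success rate with its interval (section 4.6.2) have no goal.
- Section 4.6.5 plans no additional comparisons, and section 4.6.6 only permits exploratory ones.
- The ITT comparison promised for long-term follow-up (sections 4.4 and 4.9) uses PAS ITT, which section 4.4 states is identical to mITT.

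A modest number of failed deliveries could therefore separate a pass on implanted subjects from a fail on attempted subjects, and no planned analysis would show it.

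**Working it through.** **Inputs from the documents.** 153 evaluable subjects per cohort, 62% effectiveness, and safety rates of 8% (anterior) and 12% (posterior), all from section 4.2; goals and interval method from section 4.6. **Assumed:** the number of failed deliveries k, because the documents give no rate. Data are taken as complete.

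**The plan's own figures.**

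- Sample size: 180 × 0.85 = 153.
- Effectiveness power by normal approximation: Φ[(0.12√153 − 1.96 × 0.5)/√(0.62 × 0.38)] = 0.851, matching the stated 85%. The exact rule needs at least 90/153 (lower bound 50.6%; 89/153 gives 49.9%), and P(X ≥ 90 | 153, 0.62) = 0.814.
- Safety power by the exact rule: at most 20/153 events for the 20% goal gives 0.989 at a rate of 8%; at most 27/153 for the 25% goal gives 0.985 at 12%. Both are close to the stated 99%.

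**Effectiveness with k failed deliveries counted as non-success.** The ITT denominator is 153 + k. The chance of passing on mITT and failing on ITT is P(X ≥ 90) − P(X ≥ r), where X is binomial(153, 0.62) and r is the smallest passing count out of 153 + k.

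| k | share of attempts | r / (153 + k) | P(ITT passes) | passes mITT, fails ITT |
|---|---|---|---|---|
| 0 | 0% | 90/153 | 0.814 | – |
| 2 | 1.3% | 91/155 | 0.767 | 4.7% |
| 5 | 3.2% | 92/158 | 0.714 | 10.1% |
| 8 | 5.0% | 94/161 | 0.592 | 22.2% |

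At the cut-off, 90/153 passes (50.6%) and 90/155 fails (49.9%). At the expected count, 95/153 has a lower bound of 53.9%; it still passes with ten failures (95/163, 50.3%) and fails with eleven (95/164, 49.98%).

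**If the true rate among all attempts were 50%.** This is not the null the trial states. With failure fraction f, the rate among implants is 0.50/(1 − f). The chance that mITT passes, P(X ≥ 90 | 153), is 1.8%, 2.4%, 4.2%, 7.3% and 23% at f = 0, 1, 3, 5 and 10%.

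**Safety.**

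- At the planned rates, five failed deliveries that all have events still pass: anterior 12/153 becomes 17/158 (upper bound 16.7%); posterior 18/153 becomes 23/158 (21.0%).
- With eight failures, the ITT limits are 22/161 and 29/161. If failed attempts carry three times the planned event rate (24% and 36%), the chance of passing mITT and failing ITT is 0.5% anterior and 1.6% posterior.
- Near the cut-off one event decides: 20/153 passes (19.5%) and 21/154 fails (20.1%); 27/153 passes (24.6%) and 28/154 fails (25.2%).
- Event-free failures lower the bound: 20/153 gives 19.5%, 20/156 gives 19.1%.

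**The case against.** The strongest reply is that this is a declared choice of population and not an error. Sections 2.4, 2.4.1.1, 2.6 and 4.4 consistently place the primary endpoints on implanted subjects. Failed attempts are visible elsewhere: technical success, the stent success rate with an interval, adverse events in failed attempts, and the accounting of exclusions in section 4.8. A reader could largely rebuild the effectiveness figure from these. This stands, and it is why mITT need not be displaced. A prespecified result against the goals still differs from one the reader must assemble.

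Second, the safety part changes little at the planned rates. That also stands. The sentence in section 4.4 that adds adverse events from failed attempts does not say whether they join the primary proportion. Section 2.6 points to exclusion, but the text should say so.

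Third, every failure count is assumed, and 153 is not the only possible denominator. With 180 implants the discordance for 2, 5 and 8 failures is 3.1%, 10.9% and 15.6%. With 100 implants, relevant because the posterior sample size is adaptive, it is 8.0%, 24.2% and 31.9%. The size moves; the conclusion does not.

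Fourth, the anterior indication was approved in May 2019 (synopsis and section 1.1), so nothing can be prespecified there. This limits the practical gain mainly to the posterior cohort.

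**Conclusion.** The point holds and should be fixed. Neither primary endpoint has an analysis that includes failed deliveries, although the plan defines the set that would contain them and calls those subjects treatment failures. The consequence is mainly for effectiveness. With 153 implants at a true 62%, between about 5% and 22% of trials would pass on mITT and fail on ITT if 2 to 8 deliveries failed. The expected result is robust up to ten failures. For safety the decision is secure at the planned rates and turns on single events only near the cut-off.

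These sizes rest on assumed failure counts, complete data and 153 implants. Nothing is argued from the historical rates, because the documents do not show whether they counted failed attempts.

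**What to change.** In section 4.4, for both cohorts, keep mITT as the deciding analysis and add an ITT analysis of each primary endpoint against the same goals.

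- **Effectiveness:** a failed delivery is a non-success by rule and is excluded from the regression imputation in section 4.3. That section already assigns the worst occlusion class to neurological deaths before one year, so a fixed worst-case rule is not foreign to the plan.
- **Safety:** count every adjudicated major ipsilateral stroke or neurological death after a component entered the body. For posterior subjects still in follow-up, collect primary safety status to 12 months after a failed delivery. Where follow-up ended at two months, use the available data and show two bounds for months 2 to 12: no further events, and an event in every such subject.
- **Anterior cohort:** label the ITT results supplementary.
- **Clean-up:** state whether an attempted subject counts as untreated for the replacement rule in sections 2.6, 2.6.3 and 3.3. This does not affect ITT membership.

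The cost is a few sentences plus safety contact to 12 months for the posterior subjects with a failed delivery. No success rule changes. The ITT effectiveness rate will be lower: at 3% failures, 0.62 × 0.97 = 60.1%. The chance that ITT clears 50% is 71% with five failures beside 153 implants, against 81% for mITT. Some anterior subjects may have no 12-month status. Because event-free failures ease the safety bound, the ITT safety result should sit beside the mITT result and not replace it.

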### **4.5 Primary Endpoints Justification**

#### **4.5.1 Justification for Effectiveness Criteria**

As is evident from the literature, the treatment of wide neck aneurysms with embolic coiling is generally associated with low complete occlusion rates and a high incidence of recanalization. Surgical clipping is widely perceived to be associated with high occlusion rates but greater risk of major morbidity and mortality events. However, the reliability of published data on occlusion rates following surgical clipping has recently been called into question. In a meta-analysis of surgical treatment of unruptured intracranial aneurysms conducted by Kotowksi et al—which included 60 studies published between 1990 and 2011 that described outcomes among 9,845 subjects with 10,845 aneurysms—the authors reported that occlusion outcomes were not reported for 82.2% of the aneurysms and recommended against using the results of these studies to formulate treatment plans. Quality published data on surgical clipping of wide neck aneurysms are not available.

Certain aneurysms are unable to achieve treatment success by surgery or by coiling alone. Treatment efficacy increases (increased occlusion, decreased recanalization) with the use of adjunctive devices such as stent assisted coiling as well as with more favorable aneurysm morphologies. Effectiveness outcomes based on occlusion rates, as reported in the literature, can vary widely depending on the degree of heterogeneity in the study population (which is often very high) and the methods of reporting outcomes (e.g., immediate vs. follow-up angiography results).

#### Data from the MAPS Trial

The MAPS Trial was a multinational, multicenter, randomized controlled trial conducted at 43 investigational sites and into which 626 patients with either ruptured or unruptured intracranial

## **SAfety and Effectiveness of the Treatment of Wide Neck, Saccular Intracranial Aneurysms with the Neuroform Atlas™ Stent System**

### **Short Study Name: ATLAS**

aneurysms at any location (ranging in size from 4-20 mm) were enrolled and treated using embolic coils. The original purpose of the MAPS non-inferiority trial was to compare effectiveness of Matrix-2 biopolymer-modified coils with effectiveness of bare metal coils when using a composite clinical outcome measure (i.e., Target Aneurysm Recurrence [TAR]) as the primary study endpoint. Secondary effectiveness endpoints included angiographic occlusion (as assessed by an independent Core Laboratory using the modified Raymond Scale) and clinical outcomes (as assessed using the modified Rankin Scale) (mRS). At 12-month follow-up ( $\pm$  3months), it was shown that there was no significant difference in angiographic occlusion rates or other effectiveness outcomes between the two groups. Similar findings have been reported elsewhere. In another large-scale randomized controlled trial of endovascular coiling, Molyneux et al. reported no significant difference in angiographic occlusion rates between patients randomized to treatment with polymer-loaded coils versus those randomized to treatment with bare metal coils. In a recent systematic review/meta-analysis designed to assess differences in reported unfavorable angiographic outcomes for coiled cerebral aneurysms as a function of coil type, it was similarly demonstrated that across 82 studies, there were no significant differences based on coil type.

A large proportion of patients enrolled in the MAPS trial were similar to the study population for which use of the Neuroform Atlas Stent System is intended. When key screening criteria that will be used to enroll patients into the ATLAS IDE trial were applied to the MAPS database, a total of 247 patients who underwent coiling alone were available for comparative analysis. These key criteria included: a) inclusion of wide-neck aneurysms (defined as being aneurysms having a neck width  $\geq$  4 mm or a dome-to-neck ratio  $<$  2) located in the posterior or anterior “non-petrous” circulation (i.e., excluding the petrous Internal Carotid Artery [ICA] to superior hypophyseal ICA region); b) exclusion of patients with a baseline Hunt and Hess score  $\geq$  3; and c) exclusion of patients with a baseline mRS score  $\geq$  4. In the MAPS study, of the 247 wide-neck aneurysms that met these criteria, 205 (83%) were located in the anterior non-petrous circulation and 42 (17%) were located in the posterior circulation. Within this subgroup, twelve-month ( $\pm$  3 months) angiographic data were available for 197/247 patients (80%) and were reviewed by the independent Core Laboratory that was used for the MAPS study (i.e. the University of California at San Francisco).

As the patient population comprising this subgroup closely matches the patient population to be enrolled in the ATLAS IDE trial, and the prospectively defined secondary endpoints used in the MAPS trial are similar to the effectiveness endpoints to be used in the ATLAS IDE trial, this data set of 247 patients represents a valid, reasonable and homogenous historical control group upon which performance goals can be based. Further, the major findings from the MAPS trial and other studies that examined the effect of coil type on angiographic outcome justify and support the inclusion of MAPS patients treated with either polymer-coated or bare metal coils in the comparative dataset.

**Table 3** provides a summary of angiographic outcomes in the above-described MAPS patient cohort, comparing immediate and 12 ( $\pm$  3) month occlusion outcomes by aneurysm location. At 12 ( $\pm$  3) month follow-up, total occlusion rates were slightly less than 40% and there was no significant difference in outcomes between groups of patients with anterior non-petrous and posterior circulation aneurysms.

# **Safety and Effectiveness of the Treatment of Wide Neck, Saccular Intracranial Aneurysms with the Neuroform Atlas™ Stent System**

## **Short Study Name: ATLAS**

**Table 3 - MAPS Cohort - Angiographic Outcomes as Assessed by an Independent Core Lab**

Modified Raymond Scale – Class I	Wide Neck Aneurysms [1,2] (N =247)		P-value
	Anterior Non-petrosus (n =205)	Posterior (n =42)	
12 ( $\pm$ 3) month FU or Re-intervention	37.2% (61/164)	36.4% (12/33)	0.93

[1] Neck width  $\geq$  4mm or dome-to-neck ratio  $<$  2

[2] Excludes subjects with a pre-procedure Hunt and Hess score  $\geq$  3; excludes subjects with a pre-procedure mRS score  $\geq$  4

### Data from the Scientific Literature

A comprehensive search of current scientific literature was conducted in order to identify published articles suitable for inclusion in a meta-analysis of wide neck aneurysm treatment outcomes. To be included, each published article had to meet the following key criteria: (1) English language; (2) published in 2000 or later; (3) contained data regarding safety, performance, and/or effectiveness involving the treatment of wide neck intracranial aneurysms in a clinical setting, or analyses of data maintained in registries and/or institutional databases; (4) contained data derived from a minimum sample size of n = 5; (5) could not be superseded by a publication with the same sample group, or contribute to a later publication including data from the same study (unless the article addressed a different objective); (6) contained data for complete occlusion (Raymond Score 1) rate as assessed by angiography at follow-up; (7) included literature containing data for balloon-assisted coiling; (8) included literature containing data for coiling alone; and (9) contained data from clinical and angiographic follow-up ranging from 6 to 18 months post-treatment. An important exclusion criterion was the absence of appropriate clinical or angiographic follow-up data (e.g., no long-term follow-up, or no Raymond scores reported).

The literature search yielded 339 articles using the search terms “wide neck aneurysms and occlusion”. Of these 339 articles, 329 were excluded for failing to meet the pre-determined criteria for inclusion. An additional relevant article by Hetts et al was included as it contained a subset of wide neck aneurysms treated in the Stryker sponsored MAPS Trial. This yielded 11 published articles whose data could be assessed via a meta-analysis in order to derive effectiveness performance goals for both the anterior and posterior cohorts. Stent assisted coiling data from two of these articles (Hetts et al. and Chalouhi et al.) were included in this meta-analysis. A summary of effectiveness data contained in these 11 articles is presented in Table 4.

# Safety and Effectiveness of the Treatment of Wide Neck, Saccular Intracranial Aneurysms with the Neuroform Atlas™ Stent System

## Short Study Name: ATLAS

**Table 4 - Summary of Effectiveness Data Derived from Literature Search**

Reference	N	Neck <4mm	Neck ≥4mm	Dome-to-Neck Ratio	Ruptured	Location	Coiling BAC SAC	Anz Coiled (Anz at FUP)	Immediate Complete Occlusion ALL	Immediate Complete Occlusion WNA	Complete Occlusion at Follow-Up ALL	Complete Occlusion at Follow-Up WNA	Recanaliz n /Retreatment ALL	Recanaliz n /Retreatment WNA	Time to Follow-Up Angio Mean (Range)		
2000 Aletich JNS [37]	75 anz 72 pts	52/75 (69%)	23/75 (31%)	53/75 (71%) = <2 22/75 (29%) = ≥2	20/75 (27%)	75% Ant 25% Post	100% BAC	66 anz (64 anz)	N/A	17/66 (26%)	N/A	24/64 (38%)	N/A	N/A	11.2 mo (6 - 29 mo)		
2001 Cottier AJNR [39]	45 anz 44 pts	100% Wide-neck anz			27/44 (61%)	95% Ant 5% Post	100% BAC	45 anz (45 anz)	N/A	31/45 (69%)	N/A	30/45 (67%)	N/A	N/A	16 mo (3 mo - 5 yr)		
2001 Nelson AJNR [41]	22 anz 22 pts	100% Wide-neck anz			9/22 (41%)	100% Ant	100% BAC	22 anz (20 anz)	N/A	15/22 (68%)	N/A	17/20 (85%)	N/A	0/20 (0%)	19 mo (12 - 30 mo)		
2002 Lozier Stroke [30]	495 anz 489 pts (meta-analysis of 12 studies)	40%	60% Wide-neck anz		19%	100% Post	100% Coiling	483 anz (All = 208 anz; WNA = 112 anz)	217/456 (48%)	N/A	93/208 (45%)	26/112 (23%)	46/208 22%	32/112 (29%)	16.8 mo (mean for 6/12 studies) and 26.1 mo (mean for 6/12 studies)		
2006 Niimi Stroke [31]	74 anz 70 pts	43/74 58%	10/74 (14%) = Small wide-neck 20/74 (27%) = Large (assumed to be wide-neck) 1/74 (1%) = Giant (assumed to be wide-neck)		31/74 (42%)	80% Ant 20% Post	79% Coiling 16% BAC 5% SAC	All = 74 anz; WNA = 31 anz (All = 47 anz; WNA = 25 anz)	13/74 (18%)	4/31 (13%)	10/47 (21%)	5/25 (20%)	27/47 (57%)	18/25 (72%)	12 mo (4d - 34 mo)		
2013 Chalouhi AJNR [38]	101 pts total; 32 BAC	100% Wide-neck			21/32 (66%)	81% Ant 19% Post	32/101 (32%) BAC	32 anz (32 anz)	N/A	11/32 (34%)	N/A	16/32 (50%)	N/A	5/32 (16%)	6.5 mo (3 - 36 mo)		
2013 Chalouhi AJNR [38]	101 pts total; 69 SAC	100% Wide-neck			8/69 (12%)	84% Ant 16% Post	69/101 (68%) SAC	69 anz (69 anz)	N/A	22/69 (32%)	N/A	52/69 (75%)	N/A	3/69 (4%)	8.0 mo (5 - 48 mo)		

